#### **5.3.2.4. Exposure**

No imputation will be done for first dose date or last dose date.

### **5.3.3. Imputation Rules for Date of Last Contact and Efficacy Assessments**

#### **5.3.3.1. Date of Last Contact**

The date of last contact will be derived for patients not known to have died at the analysis cut-off using the latest complete date among the following:

- All patient assessment dates (blood draws (laboratory, PK), vital signs, performance status, ECG, tumor assessments).
- Start and end dates of anti-cancer therapies administered after study treatment discontinuation.
- AE start and end dates.
- Last date of contact collected on the ‘Survival Follow-up’ eCRF (do not use date of survival follow-up assessment unless status is ‘alive’).
- Study drug start and end dates.
- Date of discontinuation on disposition eCRF pages (do not use if reason for discontinuation is lost to follow-up).

Only dates associated with actual examinations of the patient will be used in the derivation. Dates associated with a technical operation unrelated to patient status such as the date a blood sample was processed will not be used. Assessment dates after the cut-off date will not be applied to derive the last contact date.

#### **5.3.3.2. Death Date**

Partial death dates will be imputed based on the last contact date:

- If the day or both the day and the month is missing, death will be imputed to the maximum of the full (non-imputed) day after the date of last contact and the following:
  - Missing day: 1st day of the month and year of death.
  - Missing day and month: January 1st of the year of death.

### **5.3.3.3. Tumor Assessments**

All investigation dates (eg, X-ray, CT scan) must be completed with day, month and year.

If there are multiple scan dates associated with an evaluation, ie, radiological assessments occur over a series of days rather than the same day, the choice of date of assessment could impact the date of progression and/or date of response. If there are multiple scan dates associated with an evaluation, the earliest of the scan dates associated with the evaluation will be used as the date of assessment.

If one or more investigation dates for an evaluation are incomplete but other investigation dates are available, the incomplete date(s) are not considered for calculation of the assessment date and assessment date is calculated as the earliest of all investigation dates (eg, X-ray, CT-scan).

If all measurement dates for an evaluation have no day recorded, the 1st of the month is used.

If the month is not completed, for any of the investigations for an evaluation, the respective assessment will be considered to be at the date which is exactly between the previous and the following assessment. If both a previous and following assessments are not available, this assessment will not be used for any calculations.

### **5.3.3.4. Date of Start of New Anti-cancer Therapy**

Incomplete dates for start date of new anti-cancer therapy (drug therapy, radiation, surgery) will be imputed as follows and will be used for determining censoring dates for efficacy analyses and in the derivation of the end of on-treatment period.

- If the end date of new anti-cancer therapy is:
  - completely missing then it will be ignored in the imputations below.
  - partially missing with only year (YYYY) available then the imputations below will consider 31DECYYYY as the end date of the new anti-cancer therapy.
  - partially missing with only month and year available then the imputations below will consider the last day of the month for MMMYYYY as the end date of the new anti-cancer therapy.
- If the start date of new anti-cancer therapy is completely or partially missing then the imputed start date of new anti-cancer therapy is:
  - completely missing then it will be ignored in the imputations below.
  - partially missing with only year (YYYY) available then the imputations below will consider 01JANYYYY as the start date of the new anti-cancer therapy.

- partially missing with only month and year available then the imputations below will consider the first day of the month for MMMYYYY as the start date of the new anti-cancer therapy.

## 6. ANALYSES AND SUMMARIES

Refer to Section 4 for definitions of analysis sets and Section 5.2 for general methodology.

### 6.1. Primary Endpoints

#### 6.1.1. DLT

##### 6.1.1.1. Primary Analysis

The primary analyses will be based on the DLT-evaluable set. DLTs will be listed and summarized by treatment group.

### 6.2. Secondary Endpoint(s)

#### 6.2.1. Safety Endpoints

Refer to [Section 6.6](#).

#### 6.2.2. Efficacy Endpoints

The following analyses will be based on the FAS by treatment group. Assessment of response will be made using RECIST v1.1.

##### 6.2.2.1. Objective Response as Assessed by the Investigator per RECIST v1.1

The following analyses will be based on the FAS by treatment group. Assessment of response will be made using RECIST v1.1.

**Best Overall Response (BOR)** will be assessed based on reported overall lesion responses at different evaluation time points from the ‘start date’ until documented disease progression, according to the following rules:

- CR = at least two determinations of CR at least 4 weeks apart and before progression.
- PR = at least two determinations of PR or better at least 4 weeks apart and before progression (and not qualifying for a CR).
- SD (applicable only to patients with measurable disease at baseline) = at least one SD assessment (or better)  $\geq 6$  weeks after ‘start date’ and before progression (and not qualifying for CR or PR).
- Non-CR/non-PD (applicable only to patients with non-measurable disease at baseline) = at least one non-CR/non-PD assessment (or better)  $\geq 6$  weeks after ‘start date’ and before progression (and not qualifying for CR or PR).

- PD = progression  $\leq 12$  weeks after start date (and not qualifying for CR, PR SD, or non-CR/non-PD).
- Not Evaluable (NE): all other cases.

Only tumor assessments performed before the start of any further anti-cancer therapies will be considered in the assessment of BOR. Clinical deterioration will not be considered as documented disease progression.

**Objective Response (OR)** is defined as complete response (CR) or partial response (PR) according to RECIST v1.1 from start date until documented disease progression. Both CR and PR must be confirmed by repeat assessments performed no less than 4 weeks after the criteria for response are first met.

Patients who do not have an on-treatment radiographic tumor assessment (including due to early clinical progression), who receive anti-tumor treatments other than the study treatments prior to reaching a CR or PR, or who die, progress, or drop out for any reason prior to reaching a CR or PR will be counted as non-responders in the assessment of OR. Each patient will have an objective response status (0: no OR; 1: OR). OR rate (ORR) is the proportion of patients with OR in the analysis set.

ORR by treatment group will also be calculated along with the two-sided 95% CI using the Clopper-Pearson method (exact CI for a binomial proportion as computed by default by the FREQ procedure using the EXACT option).

In addition, the frequency (number and percentage) of patients with BOR of CR, PR, SD, PD, non-CR/non-PD (applicable only to patients with non-measurable disease at baseline), and NE (not-evaluable) will be tabulated. Patients with BOR of NE will be summarized by reason for having NE status. The following reasons will be used:

- Inadequate baseline assessment (includes missing assessment or non-measurable disease at baseline).
- No post-baseline assessment due to death.
- No post-baseline assessments due to other reasons.
- All post-baseline assessments have overall response NE.
- New anticancer therapy started before first post-baseline assessment.
- SD of insufficient duration ( $< 6$  weeks after start date).
- PD too late ( $> 12$  weeks after start date).

Special and rare cases where BOR is NE due to both early SD and late PD will be classified as 'SD too early'.

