19. **Tumor Assessments:** Tumor assessments will include all known or suspected disease sites. Imaging may include chest, abdomen and pelvis CT or MRI scans; brain CT or MRI scan, and bone scans (see [Section 7.4.1](#)). The CT scans should be performed with contrast agents unless contraindicated for medical reasons. The same imaging technique used to characterize each identified and reported lesion at baseline will be employed in the following tumor assessments. Antitumor activity will be assessed through radiological tumor assessments conducted at baseline, at 9 weeks then every 6 weeks, whenever disease progression is suspected (eg, symptomatic deterioration), and at the time of End of Treatment (if not done in the previous 6 weeks). Timing should follow calendar days and should not be adjusted for delays in cycle starts. Follow-up bone scans are required every 15 weeks only if bone metastases are present at baseline. Otherwise bone imaging is required only if new bone metastasis are suspected and at the time of confirmation of response for patients who have bone metastases. Assessment of response will be made using RECIST version 1.1.

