#### **6.2.2.5. Progression-Free Survival (Expansion Cohort Only)**

Progression-Free Survival (PFS) is defined as the time from start date to the date of the first documentation of objective progression of disease (PD) or death due to any cause, whichever occurs first. PFS data will be censored on the date of the last adequate tumor assessment for patients who do not have an event (PD or death), or for patients with an event after two or more missing tumor assessments. For patients who start a new anti-cancer therapy prior to an event, PFS data will be censored on the date of the last adequate tumor assessment prior to starting the new anti-cancer therapy. Patients who do not have an adequate baseline tumor assessment or who do not have an adequate post-baseline tumor assessment will be censored on the ‘start date’ unless death occurred on or before the time of the second planned tumor assessment in which case the death will be considered an event ([Table 3](#)).

In this study antitumor activity will be assessed through radiological tumor assessments conducted at screening, at 9 weeks after the first dose of study drug, and every 6 weeks until disease progression, and at the time of End of Treatment/Withdrawal (if not done in the previous 6 weeks). The allowable time window for disease assessments is  $\pm 7$  days while on treatment and whenever disease progression is suspected (eg, symptomatic deterioration).

The censoring and event date options to be considered for the PFS and DR analysis are presented in [Table 3](#).

$$\text{PFS (months)} = [\text{date of event or censoring} - \text{start date} + 1] / 30.4375$$

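### The 12-week limit for a best response of PD does not fit the week-9 and week-15 scans: PD first documented at week 15 after a missed or non-evaluable week-9 scan is tabulated as NE

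*SAP*

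**What the plan says.** **BOR rules (SAP 6.2.2.1).** The categories are hierarchical.
- CR and PR need confirmation at least 4 weeks apart.
- The next rule reads "SD (applicable only to patients with measurable disease at baseline) = at least one SD assessment (or better"), made at 6 weeks or later and before progression. Non-CR/non-PD has the same 6-week minimum.
- PD carries a limit of 12 "weeks after start date (and not qualifying for CR, PR SD, or non-CR/non-PD").
- The remainder is "Not Evaluable (NE): all other cases". Progression beyond 12 weeks ('PD too late') is one of the listed NE reasons.

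**Scan schedule.** SAP 6.2.2.5 has scans "conducted at screening, at 9 weeks after the first dose of study drug, and every 6 weeks until disease progression", with a window of 7 days either side while on treatment. The protocol fixes them to the calendar (Schedule of Activities, footnote 19): "Timing should follow calendar days and should not be adjusted for delays in cycle starts".

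**PFS rules (SAP 6.2.2.5 and Table 3, expansion cohorts only).** PD or death is an event if it follows at most one missing or inadequate assessment, or if it occurs within 15 weeks of the start date. Patients without an adequate baseline or post-baseline assessment are censored at first dose, with one exception: "unless death occurred on or before the time of the second planned tumor assessment in which case the death will be considered an event". That time is 15 weeks in Table 3.

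**The concern.** The PFS rules are tied to this trial's second planned scan and the BOR limit for PD is not. Limits of 6 and 12 weeks would suit scans at weeks 6 and 12, but here the scheduled on-treatment scans fall at weeks 9 and 15. PD first found at the second scheduled scan therefore cannot be recorded as a best response of PD. If nothing earlier qualifies the patient for SD or better, the only category left is NE.

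BOR is tabulated by dose group on the full analysis set, and the SAP itself expects those groups to be small (6.4). A patient with documented progression would appear as not evaluable in that table and, in an expansion cohort, as a progression event in the PFS table.

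**Working it through.** **Inputs.** First scan at week 9, interval 6 weeks, window 7 days either side (SAP 6.2.2.5). PD limit 12 weeks and SD minimum 6 weeks (SAP 6.2.2.1). PFS limit 15 weeks, or at most one missing assessment (SAP Table 3). First dose is Day 1, so week w is Day 7w + 1.

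**Reproducing the plan's figure.** Second planned scan = 9 + 6 = week 15, which matches the 15 weeks in Table 3.

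**Where the 12-week limit falls.**
- First window: 7 × 9 + 1 = Day 64, so Days 57-71.
- Second window: 7 × 15 + 1 = Day 106, so Days 99-113.
- PD limit: 7 × 12 + 1 = Day 85, which is 85 − 71 = 14 days after the first window closes and 99 − 85 = 14 days before the second opens.

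A second scan done within its window is always past the limit.

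**Applying both sets of rules to PD at the second scan (week 14, 15 or 16), with no other scans and no new anti-cancer therapy:**

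| Week-9 result | BOR | PFS (expansion cohorts) |
|---|---|---|
| CR, PR or SD | SD | Event |
| PD | PD | Event, dated week 9 |
| Not evaluable | NE, 'PD too late' | Event (one inadequate assessment) |
| Missed | NE, 'PD too late' | Event (one missing assessment) |

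Only the last two rows disagree. At week 16 the PD is past 15 weeks, but it is still an event because at most one assessment was missed. If weeks 9 and 15 are both missed and PD is found at week 21, BOR is NE and PFS is censored, so there is no conflict.

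PD at an unscheduled scan after Day 85, with no earlier qualifying assessment, also becomes NE (checked at week 13).

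**Size per patient.** Moving one patient from PD to NE changes each row by 1/n. Protocol 3.2 requires at least three patients at a dose before escalation and can stop at nine evaluable patients at the estimated MTD. Taking these as example group sizes, 1/3 = 33 points and 1/9 = 11 points.

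**After moving the limit to 16 weeks (7 × 16 + 1 = Day 113).** The two NE rows become PD. The other rows do not change.

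**The case against.** The case for leaving the rule alone has several sound parts.

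- **Response rate is unaffected.** Patients who progress before a CR or PR are non-responders in the full analysis set whether BOR is PD or NE. The BOR frequencies supplement that rate, and no hypothesis test is planned.
- **The patients stay visible.** 'PD too late' is tabulated as an NE reason, so a reader could add them back. Without an evaluable week-9 scan, the patient may have been stable at that time. NE is therefore a possible convention, although the SAP gives no reason for setting it at 12 weeks.
- **Other scans can fall before week 12.** The protocol requires scans when progression is suspected and at End of Treatment, about 28 days after the last dose. These will catch some progressions before Day 85 and so reduce the number affected.
- **The PFS contrast is limited to the expansion cohorts.** Dose-escalation patients have no PFS analysis to conflict with.

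All of this stands. It limits the consequence but does not explain why PD at a planned scan should be outside the PD category.

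Three stronger readings are tempting, and the documents do not support them.

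1. **That progression at the second scan is generally tabulated as NE.** It is not. SD or better at week 9 already meets the 6-week rule, so the usual patient with later PD has BOR = SD.
2. **That the SD minimum should rise to 8 weeks to match the first window, because an extra early scan can turn PD into SD.** SD seen at 6 weeks or later before progression is SD under the prespecified definition. Raising the minimum would also do harm. A patient dosed on Days 1 and 22 has an End of Treatment scan at about 22 + 28 = Day 50, which is 49/7 = 7 weeks. SD there counts now and would stop counting. PD at the 12-weekly follow-up scan, about 50 + 84 = Day 134 (19 weeks), would then be NE even with a 16-week PD limit.
3. **That SD at a very early End of Treatment scan followed by late PD is an oversight.** The SAP provides for it: "Special and rare cases where BOR is NE due to both early SD and late PD will be classified as" 'SD too early'. After one dose, SD at about Day 29 and PD at about 29 + 84 = Day 113, within 7 days either side (Days 106-120), would be only partly captured by a limit at Day 113.

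**Conclusion.** The point holds in a narrow form. The BOR limit for PD is out of line with the scan schedule, while the PFS rules in the same SAP follow it. When the week-9 scan is missed or not evaluable and no other assessment at 6 weeks or later qualifies, PD first documented at the scheduled week-15 scan is reported as NE in the BOR table. In the expansion cohorts it is also a PFS event.

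The classification follows from the SAP's definitions and day arithmetic, assuming the scan is done within its window and no new anti-cancer therapy has started. The number of patients affected cannot be derived, because the documents give no rate of missed or non-evaluable week-9 scans. The effect per patient is 11 to 33 points of the PD and NE rows at the example group sizes, and nothing on the objective response rate. This is a modest descriptive error, but it should be corrected because the correction costs almost nothing.

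**What to change.** In SAP 6.2.2.1:
- Define BOR = PD as progression at or before the second planned assessment including its window, that is, no later than 16 weeks after the start date, in patients who do not qualify for CR, PR, SD or non-CR/non-PD.
- Change the NE reason to 'PD too late' (later than 16 weeks after the start date).
- Leave the SD and non-CR/non-PD minimum, and the matching NE reason for SD of insufficient duration, at 6 weeks.
- If 12 weeks is kept, state why, and footnote the BOR table to say that PD first documented at the week-15 scan is counted under NE.

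The cost is a wording change and one constant in the BOR program, with no new data. The reported PD percentage may rise slightly. Scans done after Day 113, including some 12-weekly follow-up scans, can still give NE, so the existing rule for early SD with late PD is still needed.

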### **5.2.11. Adequate Post-baseline Tumor Assessment**

An adequate post-baseline assessment is defined as an assessment where a response of CR, PR, SD, non-CR/non-PD, or PD can be determined (see [Section 6.2.2.1](#)). Time points where the response is NE or no assessment was performed will not be used for determining the censoring date.

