#### 6.2.2.3. Duration of Response (Expansion Cohort Only)

Duration of Response (DR) is defined, for patients with OR, as the time from first documentation of objective response (CR or PR) to the date of first documentation of objective progression of disease (PD) or death due to any cause. If a patient has not had an event (PD or death), DR is censored at the date of last adequate tumor assessment. The censoring rules for DR are as described below for PFS in [Table 3](#).

$$\text{DR (months)} = [\text{date of event or censoring} - \text{first date of OR} + 1] / 30.4375$$

Kaplan-Meier estimates (product-limit estimates) will be presented by treatment group together with a summary of associated statistics including the median DR time with two-sided 95% CIs. In particular, the DR rate at 3, 6 and 12 months will be estimated with corresponding two-sided 95% CIs. The CIs for the median will be calculated according to [Brookmeyer and Crowley](#) and the CIs for the survival function estimates at the time points defined above will be derived using the log-log transformation according to [Kalbfleisch and Prentice](#) (conftype=loglog default option in SAS Proc LIFETEST) with back transformation to a CI on the untransformed scale. The estimate of the standard error will be computed using Greenwood's formula.

DR will be displayed graphically and analyzed using Kaplan-Meier methodology. If the number of patients with OR is small, the Kaplan-Meier method may not provide reliable estimates. In this case, only descriptive statistics or listings will be provided.

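### The SAP calls non-measurable disease an inadequate baseline, against its own response rules, and its duration-of-response censoring can fall before the response begins

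*SAP*

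**What the plan says.** **On non-measurable disease**

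- The BOR rules in SAP 6.2.2.1 keep a class for these patients: "Non-CR/non-PD (applicable only to patients with non-measurable disease at baseline) = at least one non-CR/non-PD assessment (or better". CR requires "CR = at least two determinations of CR at least 4 weeks apart and before progression", with no condition on measurability. PD is also open to them: progression no later than 12 "weeks after start date (and not qualifying for CR, PR SD, or non-CR/non-PD". The last class is residual: "Not Evaluable (NE): all other cases".
- SAP 5.2.10 defines an adequate baseline by three things: assessments no more than 28 days before first dose, no missing lesion assessments, and CT or MRI. For non-target lesions a recorded status is enough. Measurable disease is not required.
- SAP 5.2.11: "An adequate post-baseline assessment is defined as an assessment where a response of CR, PR, SD, non-CR/non-PD, or PD can be determined".
- The NE reasons in 6.2.2.1, applied to patients whose BOR is NE, include: "Inadequate baseline assessment (includes missing assessment or non-measurable disease at baseline".

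**On censoring**

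- SAP 6.2.2.5 sets censoring at the start date, with an exception for early death: "Patients who do not have an adequate baseline tumor assessment or who do not have an adequate post-baseline tumor assessment will be censored on the". Row 1 of Table 3 says the same, and the table's title covers both PFS and DR.
- SAP 6.2.2.3 first says that DR without an event is censored at the last adequate tumor assessment. It then adds: "The censoring rules for DR are as described below for PFS in" Table 3.
- The definition of objective response in 6.2.2.1 lists who counts as a non-responder. An inadequate baseline is not on that list.

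**The concern.** The phrase 'inadequate baseline' carries two meanings. In 5.2.10 it concerns timing and completeness. In the NE list it also takes in a disease type that the SAP elsewhere treats as assessable. The same phrase sits in row 1 of Table 3 and at the top of the censoring hierarchy in Table 4. Two programmers could therefore handle the same patient differently in BOR, in PFS, or in the table of NE reasons.

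The second problem concerns DR. The start date is a sensible earliest censoring point for PFS, whose clock starts there. The DR clock starts at the first response, so censoring at the start date gives a negative time. A negative time is not a valid Kaplan-Meier observation. The patient would have to be dropped, set to zero or reassigned, and the SAP does not say which. The patient would still count as a responder in ORR, so ORR and DR would rest on different sets of responders.

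**Working it through.** The SAP states no figure on this point to reproduce. The check compares the sections and then puts the censoring rule into the SAP's own formula.

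**1. Who reaches the NE list?** Take a patient with non-target disease only, all lesions recorded, scanned within 28 days of first dose.

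| SAP place | Result for this patient |
|---|---|
| 5.2.10 | Baseline adequate |
| 5.2.11 | A non-CR/non-PD scan is adequate |
| 6.2.2.1, BOR rules | CR, non-CR/non-PD or PD if the rule is met; NE only otherwise |
| 6.2.2.1, NE reasons | If NE, 'inadequate baseline' is available as the reason |
| Tables 3 and 4, using the 5.2.10 term | Row 1 does not apply; PFS and DR run normally |

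The conflict is between the fourth line and the others. It shows in the reason table. Suppose this patient's only usable result is progression after week 12. The patient is NE and fits both 'inadequate baseline' and 'PD too late'. The SAP settles overlap for only one pair of reasons, early SD with late PD.

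**2. What if the parenthesis were programmed as a rule assigning NE?** One confirmed CR would leave the ORR numerator. Expansion cohort sizes are not stated, so sizes are assumed. With n = 9, 1 against 0 responders is 11.1% (Clopper-Pearson 95% CI 0.3 to 48.2) against 0% (0 to 33.6). With n = 20 it is 5.0% (0.1 to 24.9) against 0% (0 to 16.8). The responder could only be a CR, because Protocol Appendix 1, Table 14 has no PR for non-target disease alone.

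**3. DR when the baseline does fail 5.2.10.** This step does not depend on measurability.

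- A baseline can fail because a lesion entry is missing or the scan is too old. The Protocol itself states the screening window two ways: 28 days before registration (Section 6.1 and the Table 2 column heading) and 28 days before treatment (footnote 1 and Appendix 1). A scan can meet the first and fail 5.2.10.
- If CR or PR is reported and confirmed, 6.2.2.1 makes the patient a responder.
- Row 1 of Table 3 then censors at the start date, even if progression is documented later. The only exception is death within 15 weeks of the start date.
- Table 3's other route to the start date, footnote b, cannot apply to a confirmed responder, because the response is itself an adequate post-baseline assessment.

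SAP 6.2.2.3: DR (months) = (date of event or censoring - date of first response + 1) / 30.4375. The start date is Day 1, and a scan at week w falls on Day 7w + 1.

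| First response | Study day | Days | DR (months) |
|---|---|---|---|
| Week 8 | 57 | 1 - 57 + 1 = -55 | -1.81 |
| Week 9 | 64 | 1 - 64 + 1 = -62 | -2.04 |
| Week 10 | 71 | 1 - 71 + 1 = -69 | -2.27 |
| Week 15 | 106 | 1 - 106 + 1 = -104 | -3.42 |
| Week 21 | 148 | 1 - 148 + 1 = -146 | -4.80 |

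Weeks 8 and 10 are the limits of the 7-day window around the first scan.

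**4. Comparison.** Take a first response at week 9 and, as an assumed example, a last adequate scan without progression at week 33. Censoring at the last adequate assessment gives ((33 - 9) x 7 + 1) / 30.4375 = 169 / 30.4375 = 5.55 months.

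**The case against.** The NE list labels patients who are already NE; it assigns nothing. Tables 3 and 4 use a term that has its own definition section, and a parenthesis in a list of reasons should not override it. All of this stands, and it rules out three inferences that a reader might draw:

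- *Non-measurable patients become NE.* Not as written: a qualifying CR, non-CR/non-PD or PD is classified before the list is reached.
- *Their PFS is censored on Day 1, which biases PFS upward.* Day-1 censoring would require the parenthesis to replace 5.2.10. Even then no direction of bias is established: selection would be on a baseline feature, and the early-death exception keeps some events.
- *The parenthesis itself produces negative DR.* That mixes two readings in one patient. Under 5.2.10 DR is positive; if the parenthesis made the patient NE, there would be no response and no DR.

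On DR, Protocol Appendix 1 says that statuses after an inadequate baseline should generally be indeterminate, which would usually prevent a response from being recorded. That makes the case rarer. It does not exclude it, because the advice is only general and BOR is built from the responses as reported. The sentence on the last adequate assessment in 6.2.2.3 points to a sensible date, but the next sentence hands censoring to Table 3, whose row 1 says otherwise.

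Reach is small. Measurable disease is inclusion criterion 2, so non-measurable cases arise only through deviation, although the SAP's full analysis set keeps every treated patient. PFS and DR are for expansion cohorts only, no hypothesis is tested, and DR may be reduced to descriptive statistics or listings if responders are few.

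**Conclusion.** Two limited defects stand.

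First, the NE reason in 6.2.2.1 contradicts the BOR rules, 5.2.10 and 5.2.11. Its direct effect is a wrong or ambiguous reason label. Any effect on BOR, ORR or PFS depends on the parenthesis being programmed as a definition, which the SAP does not instruct.

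Second, the DR rules as written censor a confirmed responder with an inadequate baseline before the response: -2.04 months for a first response on Day 64, and about -1.8 to -2.3 months across the first scan window. This assumes that a response is reported and confirmed despite the baseline failure, and that the patient does not die within 15 weeks of starting.

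A reader might also conclude that BOR and objective response should require an adequate baseline. The documents do not compel that. It is a design choice that could turn confirmed responders into NE in an all-treated analysis, and neither defect needs it.

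Few patients are likely to be affected and no formal conclusion depends on them. The wording should still be settled before the analysis is programmed.

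**What to change.** - In the NE reasons of SAP 6.2.2.1, remove the reference to non-measurable disease, and define inadequate baseline by citing 5.2.10.
- State that 5.2.10 is the only definition of adequate baseline and governs Tables 3 and 4.
- In SAP 6.2.2.3, state that the start-date provisions of Table 3 do not apply to DR, and that DR cannot be censored before the date of first response.

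The cost is three short edits to the SAP. No new data are needed, and the primary endpoint, the sample size and the response definitions are unchanged.
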